9.6 Withdrawal of Individual Subjects

A subject will be withdrawn from the study if the subject meets any of the following criteria:

- The subject is lost to follow-up
- The subject requests to be withdrawn from the study
- The subject has been found to be ineligible for participation in the study
- The Investigator (or sub-investigator) judges continuation of the study to be difficult due to AEs (e.g., hypersensitivity reactions)
- The subject is pregnant
- The subject requires tracheostomy
- The subject requires permanent assisted mechanical ventilation (≥23 hours/day)
- The Investigator (or sub-investigator) judges continuation of the study to be inappropriate due to exacerbation of the primary disease
- The subject has significant hepatic abnormalities:
 - Alanine aminotransferase (ALT) or aspartate aminotransferase (AST) >8 × upper limit of normal (ULN) OR
 - Persistent ALT or AST >5 × ULN OR
 - ALT or AST $>3 \times$ ULN with concomitant bilirubin $>2 \times$ ULN
 - Symptoms consistent with liver dysfunction (e.g., fatigue, nausea, vomiting, abdominal pain/tenderness, fever, rash, eosinophilia >5%) with concomitant ALT or AST >3 × ULN
 - Note: subjects meeting these criteria do not require withdrawal if alternative etiology is unequivocally identified on discussion with the Sponsor Medical Monitor
- Noncompliance (i.e., the subject misses more than 20% of doses in 2 consecutive dosing cycles [after consultation with MTDA or designee]).

If a subject is withdrawn prematurely from the study, the date the subject is withdrawn from the study and the reason for withdrawal will be recorded in the electronic case report form (eCRF).

If a subject drops out of the study at any time, the reason for discontinuation must be fully documented in the source documents and the eCRF. The investigator site personnel will document the AEs and any other assessments in the source documents and will make every effort to complete all required ET assessments. Study sites must follow-up with phone calls to assess for events at Weeks 12, 24, 36, and 48.

Subjects who withdraw due to liver dysfunction should be followed until resolution and assessed for alternative etiologies.

Subjects who are withdrawn from the study following enrollment may not re-enter the study.

The study may be terminated by the Sponsor at any time upon becoming aware of data that could compromise the safety and/or well-being of the subjects or for any other reason it deems appropriate.

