17.4.5 Efficacy Analysis

17.4.5.1 Primary Efficacy Analysis

Data of time from randomization in Study MT-1186-A02 to at least a 12-point decrease in ALSFRS-R or death will be included regardless of AMX0035 use (ICE1). In other words, data following AMX0035 treatment will be used in the analysis and will not be censored.

The primary efficacy endpoints associated with the study estimand will be analyzed on the randomized set using Kaplan-Meier estimates, 2-sided alpha with a nominal 20% significance level and 80% CIs. The comparison between Treatment Group 2 versus Treatment Group 1 will be performed using a log rank test with Study MT-1186-A02 randomization strata of ALSFRS-R rate of decline score from the MT-1186-A02 screening period (2 levels strata of -1,-2 or -3,-4) and the geographical region (3 levels strata of Europe, America, or Asia Pacific). Subjects without events during treatment will be right censored at the date of last study visit.

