Concomitant use of riluzole is permitted throughout the course of the study when the dose and regimen remain unchanged from the Day 1/screening visit evaluation of ALSFRS-R of Study MT-1186-A02 through the end-of-treatment (EOT) or early termination (ET) of Study MT-1186-A04. Dose reduction, dose interruption, or discontinuation due to the onset of AEs, progression of dysphagia, or gastrostomy while on oral edaravone 105 mg are allowed. The use of AMX0035 will be allowed for patients in the event that it becomes commercially available via

Mitsubishi Tanabe Pharma America, Inc.

prescription in their respective country. AMX0035 should be taken at least 1 hour after MT-1186/oral edaravone dosing.

[figure not shown]
EOT assessments will occur at Week 48 (Visit 5). For subjects who complete the double-blind treatment period, a safety follow-up telephone visit will occur at Week 50 (Visit 6).

Subjects will be allowed to change from oral administration to PEG/RIG tube administration during the study. Subjects who discontinue early from the study will complete the procedures listed at Week 48 within 7 days of discontinuation.

Site staff should also follow up via phone call at all remaining visits to complete the assessment for time to tracheostomy or permanent assisted mechanical ventilation, or death.

Further details can be found in the Study Schema (Figure 1). The schedules of assessment for each country specific (Japan) are referred to each country specific protocol.

Figure 1: Study Schema

Abbreviation: EOS = end-of-study; EOT = end-of-treatment: ET = early termination.

Day 1 is equal to the Week 48 visit of Study MT-1186-A02.

a. Subjects will receive or al edaravone at a dose of 105 mg administered once daily in each 28 Day Cycle or a dose of 105 mg administered for 10 days, followed by placebo for 18 days in each 28 Day Cycle. The dose of edaravone should be taken following an overnight fast and at least 1 to 2 hours before the morning meal.

Mitsubishi Tanabe Pharma America, Inc.

Statistical Analysis Plan Study No. MT-1186-A04 Table 1: Schedule of Activities

Assessment						
Week (window)	Dav 1	12	ੜ	36	8†	90
,	(Based on Week 48	(± 7D)	(± 7D)	(± 7D)	(± 7D)	(± 7D) Telephone Visit
	procedures from Study MT-1186-A02)	Telephone Visit		Telephone Visit	EOT/ET	EOS
Cicle	1	†	7	10		
Visit	1	č	3	t	w	9
Informed consent	Х					
Eligibility criteria	Х					
Demographics	x					
Vital signs ^c	Х		X		х	
Full Physical examination ^d	X				×	

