8.3.2. Efficacy Measures

8.3.2.1. Time to 12-point decrease in ALSFRS-R or death

The primary end point in this study is the time from the randomization date in Study MT-1186-A02 to the first occurrence of at least 12-points decrease in ALSFRS-R or death, whichever happens first.

ALSFRS-R is a questionnaire used to measure the impact of ALS that is evaluated by the Investigator. The scale measures the subjects' physical function across 12 activities of daily living. The date of the evaluation along with the results will be recorded on the eCRF with respect to "4 Handwriting" and "5 eating motion," the results for the dominant hand (the hand used in daily life at the time of screening) will be recorded.

- ALSFRS-R total score for each visit will be derived from the sum of 12 items². For the item 5 "Eating disorder," either the item (a) or (b) will be selected corresponding to subjects with or without gastrostomy respectively. The maximum total score is 4 x 12=48.
- ALSFRS-R domains Score. The following subdomain will be calculated for each visit as well as the change from baseline to week 48.
 - O Bulbar function = total of items 1 to 3
 - O Limb function = total of items 4 to 9
 - o Fine motor function = total of items 4 to 6
 - O Gross motor function = total of items 7 to 9
 - o Respiratory function = total of items 10 to 12

The time to event variable will be calculated as follows:

Time to event=Event Date or Last Observed Date – Randomization Date + 1

- The time to the first occurrence of at least 12-point decrease in total ALSFRS-R score will be calculated from randomization date in MT-1186-A02 until last total ALSFRS-R score measurement available during MT-1186-A04. If the first occurrence of at least a 12-point decrease at any visit time point is observed, then the time variable will be calculated as the difference between the date that ALSFRS-R score was observed for which the above decreased occurred and the randomization date in MT-1186-A02.
- In case of death, the time variable will be calculated as the difference between death

² Refer to Appendix I of the protocol.

Mitsubishi Tanabe Pharma America, Inc.

date and the randomization date in MT-1186-A02.

• In case the subject did not experience either of the above events, the time variable will be calculated as the difference between date of the last observed date (Censored date) and the randomization date in MT-1186-A02.

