8.3.2.2.2. ALSFRS-R score - Changes from Baseline

Changes in ALSFRS-R score (see definition in 8.3.2.1) from baseline in Study MT-1186-A02 to all post baseline visits from MT-1186-A02 until the end of Study MT-1186-A04 will be calculated for each subject where applicable.

8.3.2.2.3. Time to death, tracheostomy, or permanent assisted mechanical ventilation:

From the day of randomization in MT-1186-A02 through EOT/ET in MT-1186-A04, the Investigator (or subinvestigator) will investigate the presence or absence of the following events:

- Death
- Tracheostomy
- Permanent assisted mechanical ventilation (≥ 23 hours/day)

If any of the events are present, the following will be recorded in the eCRF; the date of the event and EOS date will be recorded. When a subject discontinues the study, study sites must follow-up with phone calls at the time points described in *Table 1: Schedule of Activities*. The evaluation results, together with the dates of the evaluation, will be recorded in the eCRF. The time to first occurrence of death, tracheostomy, or permanent assisted mechanical ventilation (defined on EMA Guideline on clinical investigation of medicinal products for the treatment of amyotrophic lateral sclerosis, 1 November 2015) will be derived as follow:

- o In case the first occurrence from at least one event mentioned above is observed any time up to the last observed visit date when MT-1186-A04 interim data base is locked, then the time variable for each subject will be calculated as:
 - The date of the event Randomization date in Study MT-1186-A02 +1
- o In case none of the events mentioned above are observed until the last observed visit date, a right censoring will be performed for each subject at the last observed date of treatment, the time variable for each subject will be calculated as:
 - Last observed Date Randomization date in Study MT-1186-A02 +1
- o Indicator (censoring) variable will be created to indicate an event (0) if the event was observed or censoring (1) if the event is not observed at interim data base lock and the subjects was either discontinued or is ongoing.

8.3.2.2.4. %Slow Vital Capacity (%SVC) - Change from Baseline

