9.2. Efficacy Analysis

For efficacy endpoints, data from MT-1186-A02 and MT-1186-A04 will be descriptively summarized and data from MT-1186-A04 only will be listed.

Survival endpoints and the other efficacy endpoints will be performed on the Randomized set and the FAS respectively. For the latter, all available assessments from both MT-1186-A02 and MT-1186-A04 will be included in the statistical models and the estimates and 95% CI will be presented at each available time point, unless other specified.

All available data regardless of use of additional/new AMX0035 treatment (ICE1) drug (except for the secondary estimand) and all available regardless of early discontinuation will be included.

[figure not shown]

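### SAP 8.3.2.2.3 gives two censoring dates for time to death, tracheostomy or permanent ventilation; followed literally, the text lowers event-free estimates in both arms

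*SAP*

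**What the plan says.** SAP 8.3.2.2.3 derives the composite in three bullets.

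- **Events.** An event counts if it is "observed any time up to the last observed visit date when MT-1186-A04 interim data base is locked". This window is not limited to treatment.
- **Censoring.** A subject with no event up to the last observed visit date falls under the rule that "a right censoring will be performed for each subject at the last observed date of treatment". The formula beneath reads "Last observed Date Randomization date in Study MT-1186-A02 +1" (the minus sign is lost in text extraction). The section does not define the last observed date.
- **Indicator.** Subjects without an event at the interim lock are coded as censored, whether discontinued or ongoing.

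Other places bear on which date is meant.

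- SAP 4.1, on early discontinuation: "Site staff should also follow up via phone call at all remaining visits to complete the assessment for time to tracheostomy" and the other component events. Protocol 9.6: "Study sites must follow-up with phone calls to assess for events at Weeks 12, 24, 36, and 48".
- SAP 9.2, on efficacy data: "all available regardless of early discontinuation will be included".
- SAP 8.3.2.1 ends event-free time for the primary endpoint at the last observed date and does not mention treatment. Protocol 17.4.5.1: "Subjects without events during treatment will be right censored at the date of last study visit".
- The opening of SAP 8.3.2.2.3, like Protocol 12.2.2, has investigators look for these events only through EOT/ET in A04. A few lines later it requires phone calls after discontinuation.

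**The concern.** One bullet supports two different derived times. The formula does not settle the matter by itself, because its undefined date can be read as shorthand for the phrase just above it.

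The end-of-treatment reading is also asymmetric. A subject who stops treatment and later dies keeps all the time up to death. A subject who stops and is known from phone calls to be event-free loses all the time after stopping. Whether off-treatment time is kept then depends on the outcome. Risk sets are too small while the event count is unchanged, so the estimated hazard is too high and event-free estimates are too low.

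The variable feeds this composite's stratified log-rank test (SAP 9.2.2.1.3), its Cox and RMST analyses (SAP 9.2.2.1.3.1) and its subgroup analyses (SAP 9.4). SAP 9.2.2.1.3.1 also analyses each component separately, and SAP 8.3.2 gives those times no derivation of their own.

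**Working it through.** **No plan figure to reproduce.** The documents state no rate, power or event count for this composite.

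**One subject.** Use the nominal days of SAP Table 5 and take randomization as Day 1. A subject stops treatment at A04 Week 12 (Day 421) and is phoned, event-free, to A04 Week 48 (Day 673). The text gives 421 days and the formula 673 days, a difference of 673 − 421 = 252 days.

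**Direction, in closed form.** Assume exponential event times (hazard λ), independent exponential treatment stopping (hazard μ), and full phone follow-up to W = 96 weeks. Write S(t) = exp(−λt) and G(t) = exp(−μt). Under the literal text the fraction at risk at t is S(t) − S(W)[1 − G(t)], because event-free subjects who have stopped treatment are removed and future events are not. The Kaplan-Meier estimate at W then tends to

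exp{ −∫₀ᵂ λS(t) / ( S(t) − S(W)[1 − G(t)] ) dt }.

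Mean follow-up per subject is (1 − S(W))/λ under the formula. Under the text it is lower by S(W)(W − d/μ), where d is the proportion stopping by Week 96. Example with S(W) = 0.70 and d = 0.20:

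- λ = −ln 0.70/96 = 0.003715 and μ = −ln 0.80/96 = 0.002324.
- Formula: 0.30/0.003715 = 80.75 weeks.
- Text: 80.75 − 0.70 × (96 − 86.04) = 73.78 weeks.
- Crude hazard inflation: 80.75/73.78 = 1.094.

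| True event-free at Week 96 | Stopping by Week 96 | Estimate, literal text | Crude hazard inflation |
|---|---|---|---|
| 0.70 | 10% | 0.688 | 1.044 |
| 0.70 | 20% | 0.674 | 1.094 |
| 0.70 | 30% | 0.657 | 1.152 |
| 0.70 | 40% | 0.637 | 1.220 |
| 0.80 | 10% | 0.791 | 1.048 |
| 0.80 | 20% | 0.780 | 1.102 |
| 0.80 | 30% | 0.768 | 1.165 |
| 0.80 | 40% | 0.752 | 1.240 |

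Censoring at the last observed date returns 0.70 or 0.80. A simulation of 400,000 subjects agrees with these estimates to within 0.002.

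**The trial as stopped.** SAP 5.2 says that no final analysis will be done, so full follow-up to Week 96 overstates the effect. The only anchor is SAP 4.2: 202 of 384 randomized subjects entered A04, so 384 − 202 = 182 (182/384 = 47.4%) did not, for any reason.

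A second simulation (5,000 replicates per scenario) assumed 192 subjects per arm, a true hazard ratio of 1, 10% or 25% composite events by Week 48, and calls every 12 weeks. The study cut was set so that about 202 subjects are event-free and on treatment past Week 48. The A02 protocol is not supplied, so both cases are shown for subjects who left during A02: phoned to Week 48, or not phoned. The hazard-ratio columns give the ratio of the estimate under the text to that under the formula.

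| Discontinuation reached by | A02 leavers phoned | Drop at Week 96, equal 20% or 30% (points) | Hazard ratio, equal | 30% vs 20% | 40% vs 20% | Event-free subjects whose time changes |
|---|---|---|---|---|---|---|
| Week 96 | yes | 0.6–1.9 | 1.00 | 1.02–1.03 | 1.05–1.06 | 36–64 |
| Week 96 | no | 0.2–0.6 | 1.00 | 1.00 | 1.01 | 7–12 |
| Week 48 | yes | 1.3–4.1 | 1.00 | 1.05 | 1.12 | 70–123 |
| Week 48 | no | 0.4–1.3 | 1.00 | 1.01 | 1.01–1.02 | 13–23 |

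The heaviest scenario sits at the limit of the anchor: 25% events and 30% mean discontinuation by Week 48 leave 384 × 0.75 × 0.70 = 201.6 subjects.

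**The case against.** The best reply is that the plan already gives a workable answer. The bullet contains an explicit formula, and a programmer would most likely code it. The primary endpoint uses the same expression, the composite is to be analysed similarly, and SAP 9.2 keeps data regardless of early discontinuation. The indicator bullet treats discontinued and ongoing subjects alike. Where the SAP means the last dose, as in the exposure formula of SAP 8.3.1.4, it says so, so *of treatment* may loosely mean the treatment period. This stands as evidence of intent. It does not make the written rule consistent, and the sentence that ends event assessment at EOT/ET gives some support to the other reading.

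A second reply is that the event bullet never says whether a phone call after discontinuation is a visit, so the asymmetry is partly inferred. That is fair. SAP 4.1 and 9.2 favour counting such events, but the event window needs the same clarification as the censoring date.

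A third reply is that the sizes are all assumed, and that stopping is modelled as independent of events. Protocol 9.6 withdraws subjects for tracheostomy, permanent ventilation and disease exacerbation, so in practice stopping follows the endpoint. This also stands.

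A reader might go further and infer that the treatment comparison is biased. The documents do not support that. The hazard-ratio shifts above arise from an assumed imbalance in discontinuation, and no passage reports or predicts one. With equal 30% discontinuation and true hazard ratios of 0.6, 0.775 or 1, the hazard ratio moved by at most 0.5%.

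**Conclusion.** The inconsistency is real: the text and the formula of one bullet give different dates, and the formula's date is undefined. The formula is probably what was meant, so the plan should not be read as having chosen to censor at end of treatment. The literal rule would nevertheless be wrong. It would lower Kaplan-Meier and RMST estimates in both arms, with no imbalance needed.

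The size is unknown. Under the assumed rates for the early-stopped trial, the drop at Week 96 is 0.2 to 4.1 percentage points with equal discontinuation, and the hazard ratio is unchanged. The 1.12 at the top of the range needs 40% versus 20% discontinuation by Week 48 and phone follow-up of subjects who left during A02; neither is documented.

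The primary endpoint has its own censoring rule in SAP 8.3.2.1 and is not touched. This composite is secondary, with nominal p-values and no testing order (SAP 9.2.2), so no decision rule changes. The correction should be made because the derivation is wrong as written and cheap to repair, and because no later analysis is planned in which it could be put right.

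**What to change.** In SAP 8.3.2.2.3:

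1. Delete *of treatment* from the censoring bullet.
2. Define one date for both bullets: the last date, on or off treatment, at which event status is known from a visit or phone contact, up to the data lock. Count events up to that date and right-censor event-free subjects at it.
3. Reconcile the opening sentence, which ends event assessment at EOT/ET, with the phone follow-up required after discontinuation.
4. State that the same date applies to the component times in SAP 9.2.2.1.3.1 and to the composite's log-rank, Cox, RMST and subgroup analyses.

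The cost is two words deleted and a few sentences added or aligned. No new data are needed, because SAP 8.3.2.2.3 already has the results and dates of the follow-up evaluations recorded in the eCRF.

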8.3.2.2.5. Body Weight - Change from baseline in Body Weight

Body weight will be recorded in pounds or kilograms. Changes from baseline in MT-1186-A02 to all post baseline visits from MT-1186-A02 until the end of Study MT-1186-A04 will be calculated for each subject where applicable.

8.3.2.3. King's ALS Clinical Stage Derived from ALSFRS-R Score and Death Event

The King's ALS Clinical Staging System describes functional progression of ALS in terms of magnitude of disease involvement of different CNS regions (bulbar, upper limb, lower limb, need for gastrostomy and need for tracheostomy); according to its developers, the system was designed to inform patient-care decision making, resource allocation, research classifications, and clinical trial design¹¹. Stages 1, 2, and 3 refer to the number of CNS regions (bulbar, upper limb, lower limb) involved at assessment, as described in *Table 4* below. Stage 4A is defined solely by impairment of swallowing sufficient to require gastrostomy, and Stage 4B is defined solely by respiratory involvement sufficient to require ventilatory support. Functional involvement of three CNS regions is not a prerequisite to Stage 4A or 4B.

While the King's ALS Clinical Staging System was designed initially for use as an assessment tool to be used in clinic, Balendra and colleagues 12 developed a method for estimating King's ALS Clinical Stages based on responses to ALSFRS-R items Q1 (speech), Q2 (salivation), Q3 (swallowing), Q4 (handwriting), Q5A/Q5B (self-feeding), Q8 (walking), Q10 (dyspnea), and Q12 (respiratory insufficiency) 12. The algorithm for mapping from responses to these items to King's Stage is also described in *Table 4*.

Table 4: King's ALS Clinical Staging System

King's Stage	Definition	Item Mapping
1	Functional involvement of 1 CNS region	Bulbar involvement Score ≤3 on Q1, Q2, or Q3
2	Functional involvement of 2 CNS regions	Upper limb involvement Score ≤3 on Q4 or Q5A
3	Functional involvement of 3 CNS regions	Lower limb involvement Score ≤3 on Q8
4A	Need for gastrostomy	If Q5B is answered, rather than Q5A
4B	Need for non-invasive ventilation	Score of 0 on Q10 or score ≤3 on Q12
_5	Death	

CNS: Central nervous system regions are bulbar, upper limb, and lower limb

Mitsubishi Tanabe Pharma America, Inc.

Since the MT-1186-A02 and MT-1186-A04 clinical trials will not collect information on King's Stage directly, ALSFRS-R item responses and patients' survival will be mapped to stages for every ALSFRS-R collected visit using the above published algorithm and patientlevel data. Patients with baseline ALSFRS-R assessments at MT-1186-A02 that will not meet criteria for lower limb, upper limb, or bulbar involvement, and that also will not have evidence of Stage 4A or Stage 4B, will be designated "Stage 0", as their assessments could not be mapped to the King's ALS Clinical Staging System. For the King's stage derivation, the available ALSFRS-R data at each analysis visit will be used in the subjects who were not dead. If the subject was reported as death from the last observation visit to last day of the nearest analysis visit window, the King's stage from the analysis visit will be Stage 5. If a subject not reported as death will have missing ALSFRS-R assessment at each visit, the last observation will be carried forward for the last King's stage value: In the vast majority of circumstances patients will either remain in the same clinical stage from one assessment to the next or they will experience a decline in stage. In those relatively rare instances, in which subject will be found to improve from one assessment to the next, the value from their immediately prior assessment will be used rather than the actual observed value, because the improvement will be considered to be temporary or spurious.

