8.4. Analysis Visit Definitions

The acceptable visit dates windows of observation, examination, and investigation are specified as in Table 5: The analysis visit windows. Data obtained within the acceptable windows will be used for analysis or presentation. If the dates of observation, examination, or investigation are out of the following acceptable range, data obtained on those days will not be used for analysis or summary statistics. However, all data as captured will be listed. The date of the first dose of study drug in MT-1186-A04 is defined as A04 Day 1. Unless otherwise specified, baseline will be the last observed value of the parameter of interest prior to the first intake of study drug in MT-1186-A02 (this includes unscheduled visits). For other visits, if there are multiple data in a window, the closest data to nominal day will be used. If the distance to the nominal day is the same, the data of later date will be used.

Mitsubishi Tanabe Pharma America, Inc.

Table 5: The analysis visit windows

Analysis visit	Nominal day	Window		
		Except for laboratory test in Japan site	Laboratory test in Japan site	
Day 1 (A02)	Day 1	≤Day 1		
Day 8 (A02)	Day 8	-	Day 2 to 11	
Week 4 (A02)	Day 29	Day 2 to 42	Day 23 to 42	
Week 8 (A02)	Day 57	Day 43 to 71		
Week 12 (A02)	Day 85	Day 72 to 127		
Week 24 (A02)	Day 169	Day 128 to 211		
Week 36 (A02)	Day 253	Day 212 to 294		
Week 48	Day 337	Day 295 to 379		
(A02 and A04 Day 1)				
Week 60 (A04 Week 12)	Day 421	Day 380 to 462		
Week 72 (A04 Week 24)	Day 505	Day 463 to 546		
Week 84 (A04 Week 36)	Day 589	Day 547 to 630		
Week 96 (A04 Week 48)	Day 673	Day 631 to 715		

In case assessments are done at the Early Termination visit, these assessments will be used as data for the scheduled visit closest to the early termination time point, in case the corresponding data are missing from this visit.

Mitsubishi Tanabe Pharma America, Inc.

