9.2.2.2.3. King's ALS Clinical Stage Derived from ALSFRS-R Score and Death Event

King's ALS Clinical Stage analysis will be done using the FAS. A shift table to each visit throughout the periods of both MT-1186-A02 and MT-1186-A04 from baseline category will be summarized using number and percentages.

Mitsubishi Tanabe Pharma America, Inc.

For the Kings ALS Clinical Staging System, attention will focus on two events of clinical progression:

- Any decline in stage from baseline
- Any \geq 2-stage decline from baseline

These events will be analyzed in terms of both the proportion of patients who will experience the events between baseline and visit Week 96 (A04 Week 48) in MT-1186-A04 using chi square test for proportions, as well as the time to these events using stratified log rank test using the randomization strata of ALSFRS-R rate of decline score during the screening period (2 levels strata of -1,-2 or -3,-4), Geographical Region (3 levels strata of Europe, America or Asia Pacific). For the latter, study dropouts prior to any event will be treated as censored as of the date of their first missing assessment. The time to event will be also displayed using the Kaplan Meier figure. Comparisons will be made between treatment groups on an overall basis, as well as controlling for King's stage at baseline using Cochran–Mantel–Haenszel test (CMH).

Mitsubishi Tanabe Pharma America, Inc.

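### King's-stage time-to-event analyses censor dropouts whose later death is on record, and the Stage 5 rule does not say to which visit a death belongs

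*SAP*

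**What the plan says.** King's stage is an exploratory endpoint (SAP 3.3.3) with death as Stage 5 (King's staging table, SAP 8.3.2.3). SAP 9.2.2.2.3 tests two events, any decline in stage and a decline of two or more stages from baseline. Each is analysed as a proportion up to Week 96 and as time to event by stratified log-rank test. For the time-to-event analysis, "study dropouts prior to any event will be treated as censored as of the date of their first missing assessment".

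The protocol keeps looking for deaths after a subject leaves A04. Section 9.6 states: "Study sites must follow-up with phone calls to assess for events at Weeks 12, 24, 36, and 48". Section 12.2.2 and the footnote to Table 1 name death among those events. The opening of SAP 9.2 says that available efficacy data are included regardless of early discontinuation.

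The stage at each visit comes from three sentences in SAP 8.3.2.3:

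- Living subjects: "the available ALSFRS-R data at each analysis visit will be used in the subjects who were not dead".
- Deaths: if death is reported "from the last observation visit to last day of the nearest analysis visit window, the King's stage from the analysis visit will be Stage 5".
- Missing scores: "If a subject not reported as death will have missing ALSFRS-R assessment at each visit, the last observation will be carried forward".

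The windows are in SAP 8.4, Table 5.

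**The concern.** Death is the worst category of this endpoint and part of its name. Under the censoring sentence, a subject who leaves A04 without a decline and is later found to have died contributes no event, although the date of death is recorded. Protocol 9.6 lists exacerbation of the primary disease, tracheostomy and permanent ventilation among the reasons for withdrawal. Dropouts are therefore likely to be at higher risk of death, and censoring them before a known death is informative.

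The second problem is in the visit tables. The word *nearest* has no stated reference point: it could mean nearest to the death or nearest to the last observation, and looking forward or in either direction. Nor is any order of precedence given between a stage scored while the subject was alive and a death later in the same window. Two programmers could place the same death at different visits, and the choice could end up being made after unblinding.

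**Working it through.** The plan gives no figure to reproduce. The check sets the rules against Table 5 of the SAP.

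**Inputs (SAP 8.4, Table 5).**

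| Visit | Nominal day | Window (days) |
|---|---|---|
| Week 48 (also A04 Day 1) | 337 | 295–379 |
| Week 60 (A04 Week 12) | 421 | 380–462 |
| Week 72 (A04 Week 24) | 505 | 463–546 |
| Week 84 (A04 Week 36) | 589 | 547–630 |
| Week 96 (A04 Week 48) | 673 | 631–715 |

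**1. Death after dropout.** Take a subject in A04 with no decline so far, last ALSFRS-R at Week 60 (Day 421), who then discontinues and dies on Day 600.

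- The death falls between the A04 Week 36 call (Day 589) and the A04 Week 48 call (Day 673), so the latter should find it.
- The first missing assessment is Week 72. If it is dated by its nominal day (an assumption, as the SAP gives no rule), censoring is on Day 505.
- 600 − 505 = 95 days. The subject leaves the risk set 95 days before a recorded death, and the death is not an event.

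None of this uses the word *nearest*. It affects only subjects who had not yet had the event in question when they dropped out. Death is a decline from every living stage. It is also a decline of two or more stages from Stage 3 or below, if 4A and 4B count as one step (the SAP does not say).

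**2. Death soon after an attended visit.** Take a subject scored on Day 337 who enters A04 and dies on Day 375.

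- 375 ≤ 379, so the death lies in the Week 48 window. Week 48 is also the nearer nominal day: 375 − 337 = 38 days, against 421 − 375 = 46 days to Week 60.
- If *nearest* means nearest to the death, the subject becomes Stage 5 at Week 48. That visit is also A04 Day 1, and the stage scored there is overwritten.

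**3. What each reading of *nearest* does**, for a last ALSFRS-R on Day 421:

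| Reading | Deaths placed on the visit already scored | Deaths not covered |
|---|---|---|
| A. Window containing the death | Days 422–462 | none |
| B. Next window after the last observation | none | from Day 547 (more than 546 − 421 = 125 days later) |
| C. Window of the last observation | Days 422–462 | from Day 463 |
| D. First scheduled visit on or after death | none | none up to Day 673; no later visit exists after that |

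Under B and C an uncovered death is also outside the carry-forward rule, which is worded for subjects not reported as dead.

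**4. Exposure under reading A.** From Week 12 to Week 96 there are 7 × 84 = 588 days between nominal visits. Days after a nominal day but still in that visit's window number 42 + 42 + 41 + 42 + 41 + 41 + 41 = 290, and 290/588 = 49%. If every visit is 7 days late the share is 241/588 = 41%, and if 7 days early 339/588 = 58%. This is a share of calendar days. It is a share of deaths only if deaths are spread evenly between visits.

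**The case against.** **Precedence may already be implied.** A subject scored on Day 337 was not dead at that visit, so the sentence on living subjects can be read as keeping the observed stage. This is a fair reading, and it removes the overwriting. It is not stated, though, and the Stage 5 sentence that follows carries no exception. SAP 8.4 does not settle the matter: "if there are multiple data in a window, the closest data to nominal day will be used" chooses among assessments and does not rank a death against a score.

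**A reader might infer that deaths must be either back-dated or lost.** The documents do not support that. Reading D does neither up to Day 673. Nor does the rule if it is applied visit by visit with the observed stage taking precedence. A reader might also turn the window lengths into a percentage inflation of Stage 5. Such a figure would need reading A, no precedence for the observed stage, on-time visits and a constant low hazard, and it would multiply an unknown count.

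**The censoring sentence may mean dropouts with no event at all, or may be a deliberate exception to SAP 9.2.** Either is possible. However, the wording turns on whether dropout came before the event, which includes a subject who drops out and then dies, and no exception is declared or justified.

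**The reach is small.** This objection stands. The endpoint is exploratory, with no type I error correction. SAP 8.3.2.1 dates deaths directly in the primary endpoint ("In case of death, the time variable will be calculated as the difference between death" date and A02 randomization), and SAP 8.3.2.2.3 does the same for the survival composite. Of 384 randomized subjects, 202 had entered A04 when the SAP was signed (SAP 4.2). Both studies were stopped, and only the interim A04 analysis remains (SAP 5.1, 5.2).

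**Conclusion.** The concern holds in two parts, with different certainty.

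The first does not depend on how *nearest* is read. As worded, SAP 9.2.2.2.3 excludes from the King's-stage time-to-event analyses a death recorded after an A04 discontinuation. This conflicts with the general inclusion rule in SAP 9.2 and with the purpose of the follow-up calls. It is shown only for A04 discontinuations, because the A02 protocol is not among the documents and post-dropout follow-up in A02 cannot be checked.

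The second is an ambiguity and not a proven misdating. The Stage 5 sentence allows readings that overwrite a stage scored in life, and others that do not. The SAP also does not say whether a death enters the time-to-event analysis on its own date or on a visit date, so misdating there cannot be asserted.

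The number of affected deaths is not in the documents, and nothing in them shows an effect that differs between arms. The primary and survival endpoints are untouched. This is worth correcting because the change is nearly free, but no main conclusion depends on it.

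**What to change.** 1. In SAP 9.2.2.2.3, count any recorded death, including one after dropout, as an event on the actual date of death. Censor at the first missing assessment only those dropouts with no recorded death.
2. In SAP 8.3.2.3, replace the Stage 5 sentence with wording such as:

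> At any analysis visit with an ALSFRS-R assessed before death, the observed stage is kept. At every later analysis visit without such an assessment whose window ends on or after the date of death, the stage is 5, however long after the last ALSFRS-R the death occurred. A death after the Week 96 assessment is counted in the time-to-event analysis and reported separately from the Week 96 shift table.

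3. Add that carry-forward also applies, in a subject who later dies, at unassessed visits whose window closed before the death. In the first example that is Week 72 (window to Day 546), and Stage 5 then starts at Week 84.

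This wording also covers a death between an early visit and its nominal day: for a subject scored on Day 331 who dies on Day 335, the Week 48 score stays and Stage 5 starts at Week 60.

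The cost is a few sentences of SAP text and a small programming change. Dates of death are already collected, so no new data are needed. The wording should be settled before the analysis is unblinded.
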